1.6 Study Variables

A. Independent Variables, Interventions, or Predictor Variables

The primary independent variable will be group (emotional or rational condition).

Emotional Appeal: Participants will be presented with a short vignette about a child undergoing cancer treatment and needing a bone marrow transplant in order to survive cancer. A publicly available animation of a teddy bear and hospital tools is also included in this condition.

Rational Appeal: Participants will be presented with data regarding the importance of considering race/ethnicity when looking for a bone marrow transplant donor and the likelihood of finding a match based on the patient's racial/ethnic background. An infographic depicting this information was created for this study.

Secondary Independent Variables: Additionally, demographic factors (race/ethnicity, sex, age), Altruism, Self-Esteem and Knowledge will be tested as secondary independent variables.

A full list of study measures is included in Appendix B.

Construct/Measure Name	Description
Demographics	(8) items will be used to assess the demographics of the student population.
Altruism	The Self-rated Altruism Scale (20 items) assesses altruistic behavior. Specifically, the questions refer to certain altruistic actions that students have partaken in and their frequency of said activities (Rushton, Chrisjohn, & Fekken, 1981).
Self-Esteem	The Rosenberg Self-Esteem Scale (10 items) tests the self-worth of an individual by testing the negative and positive feelings about ones' self using a 4-point Likert scale (Rosenberg, 1965).
Social Desirability	The Marlowe Crown Social Desirability Index short form (13 items) will be used to assess how much student responses are influenced by demand characteristics of participating in research (Fischer & Fick 1993).
Healthcare Distrust	The Healthcare Distrust Scale (10 items) assesses the level of trust participants have in the healthcare system. Specifically, the scale covers the positive and negative aspects of the healthcare system and how trust impacts choices (Rose et al., 2004).
Knowledge	This knowledge measure tests (12 items) misconceptions about the bone marrow registry and will be used to assess the general knowledge of the population we are administering the survey in to see the depth of knowledge regarding the research topic. This survey will also assesses opinions of participants regarding the process of going through a bone marrow transplant (Vasconellos 2011).
History of transplant/donation	Previous research by Narayanan et al., (2016) has included these 15 items to assess an individual's familiarity with the transplant and donation process.
Motivations to donate	Participants are asked to rank order 11 possible reasons that they may decide to register for the transplant registry (Bart et al., 2014). Participants will complete this measure before and after the Emotional/Rational condition presentation.
Attitudes towards bone marrow transplant	Participants will be asked 9 questions about their attitudes towards joining the bone marrow registry and donating stem cells at a later date. This measure has been used in previous research (Narayanan et al., 2016).
Ambivalence	The Simons Ambivalence Scale is a 7-item scale developed to assess feelings about solid organ donation(Gardner, 1987). The measure has been modified for stem cell donor participation (Fingerut et al., 2020) and 4 of the 7 items will be used in the current study.

B. Dependent Variables or Outcome Measures

The primary dependent variable is intentions to register in the bone marrow transplant registry.

Secondary Dependent Variables: Participants will be asked about how factual and how emotional they perceived the appeal they received is to determine if the manipulation worked. We will also ask about their current mood again.

Construct/Measure	Description
Intentions to register	Participants will be asked 2 questions about whether they will register and the rate the likelihood of registering. They will be asked these questions before and after the experimental manipulation.
Manipulation Check	Participants will be asked to rate how emotional and how factual the appeal they received was on a 1-7 scale.
Mood	Participant mood will be assessed pre/post survey, asking participants to rate their current mood on a 1-10 scale.

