1.0 Research Design

1.1 Purpose/Specific Aims

The current study seeks to understand factors that influence college students' likelihood of participating in the National Marrow Donor Program (NMDP)/Be the Match for bone marrow and stem cell donations. The secondary aim is to compare emotional and rational approaches to encouraging participation in the registry and how these approaches may impact intentions to participate in the NMDP.

A. Objectives

1. The study will describe the role of demographic, personality, and psychosocial factors in attitudes towards participating in the National Marrow Donor Program.
2. Two strategies for increasing motivation (emotional appeal or factual data on racial/ethnic disparities in representation on the registry) for enrollment will be tested.
3. Strategies for enrollment will be compared by Race and Ethnicity to understand the best approaches to recruiting diverse students into the registry program.

B. Hypotheses / Research Question(s)

Approximately 12,000 patients need a bone marrow transplant each year to treat their cancer or other hematologic condition, but only about 30% of these patients find matches within their families (National Marrow Donor Program, 2013). The NMDP maintains a list of potential donors through the "Be the Match" organization which often runs donor drives on college campuses. Bone marrow donors are matched on genetic similarities, making race and ethnicity an important component in finding a match between a patient and a potential donor. Donors registered with Be the Match are 67% White, making it more difficult for individuals of color to find good matches, which may delay transplants and ultimately impact survival and the success of transplants. Thus, diversity is an important component of enrolling potential donors in the transplant registry. Because the student body of Rutgers Camden is diverse and within the age range targeted to join the NMDP, understanding psychological factors that contribute to participation and the most effective strategies to cultivate enrollment intentions is an important step towards enhancing the diversity of the donor registry and improving health outcomes for patients of color.

1. It is hypothesized that students who report high levels of altruism will be more likely to report an intention to enroll in the stem cell transplant registry.

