2. It is hypothesized that students who report high levels of knowledge about stem cell transplants will be more likely to report an intention to enroll in the stem cell transplant registry.
3. It is hypothesized that high altruistic students will be more likely to enroll when presented with an emotional appeal.
4. It is hypothesized that high knowledge students will be more likely to enroll when presented with a factual appeal.
5. It is hypothesized that the rational appeal which focuses on health disparities will result in a higher likelihood of enrollment for students of color as compared to white students.
6. It is hypothesized that self-esteem will differ between individuals who do and do not indicate an intention to enroll in the registry.

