1.3 Research Design and Methods

A. Research Procedures

This study is a randomized controlled trial that will randomize participants to receive either an emotional appeal about a child with cancer who needs a bone marrow transplant or a rational appeal using data on the racial/ethnic disparities within the transplant registry. (See Appendix A for condition prompts).

Participants will be recruited through the Psychology Subject Pool through the SONA system which will then link students to the study measures in Qualtrics. Participants will be asked their age to confirm eligibility to participate (students must be between 18-35) and eligible students will be presented with the consent form in Qualtrics. Participants will then be asked to complete measures of demographic information, personality/psychological characteristics, and transplant-related knowledge, intentions, and attitudes. All participants will then be given background information on bone marrow transplants (See Appendix A for text).

Randomization: Students will be randomized by sex in Qualtrics to the emotional presentation condition or the rational presentation condition. The emotional condition will tell the story of a fictional pediatric patient with cancer who needs a transplant. The rational condition will describe the facts about the need for diversity in the registry (See Appendix A for condition prompts).

After being presented with the rational or emotional appeal, participants will again be asked their intentions to register, their motivations for registering, and their mood.

B. Data Points

Study data will include demographic information and responses to questionnaires given during the survey in Qualtrics.

C. Study Duration

Participation will last approximately 30 minutes.

D. Endpoints

The study will continue to collect data until a sufficient sample size is accrued.

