1.5 Sample Size Justification

Prior research has demonstrated an effect size of $w=0.38$ (medium effect) between an emotional and rational appeal, thus we expect a medium effect size (Studts et al., 2010). In order to compare the effect of the two conditions (emotional/rational) by race/ethnicity (White, African-American, Latinx considered as the primary groups represented, recognizing there will be others) we will need 300 participants to have 85% power to detect a medium effect with a p-value of 0.05. To be conservative and ensure we have a large enough sample of each race/ethnicity group, we will seek to enroll 400 students.

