6.0 Data Management Plan

6.1 Data Analysis

Data will be analyzed using ANOVAs and multivariate linear regression models.

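### Section 6.1 does not say how the pre-appeal intention answer is used; naming it as a covariate (ANCOVA) is a free precision gain, mainly for the condition effect by race/ethnicity

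*Combined protocol and SAP*

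**What the plan says.** Section 1.6 B names intention to register as the primary dependent variable and describes two items: "Participants will be asked 2 questions about whether they will register and the rate the likelihood of registering". On timing it adds: "They will be asked these questions before and after the experimental manipulation". Section 1.3 A gives the order. Intentions are collected with the other questionnaires, then "All participants will then be given background information on bone marrow transplants", then students are randomised by sex to one of the two appeals, and then "participants will again be asked their intentions to register, their motivations for registering, and their mood".

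The list of independent variables in section 1.6 A has condition, demographic factors, altruism, self-esteem and knowledge. It does not have pre-appeal intention. The analysis plan in section 6.1 is one sentence: "Data will be analyzed using ANOVAs and multivariate linear regression models".

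Section 1.5 sizes the study for the two conditions by race/ethnicity: "we will need 300 participants to have 85% power to detect a medium effect with a p-value of 0.05". The enrolment target is then raised to 400. Hypothesis 5 in section 1.1 expects the rational appeal to give a "higher likelihood of enrollment for students of color as compared to white students".

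**The concern.** A baseline value of the primary outcome is collected before randomisation, but no section says whether it is a covariate, is subtracted, is a repeated factor or is ignored. Section 1.6 also does not say which of the two items, or which time point, is the primary outcome.

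Three analyses of the rating fit section 6.1: post-appeal value only, change score (or repeated-measures ANOVA), and ANCOVA. They differ in precision. With two items, that leaves at least six routes to the primary result, and the choice could be made after the data are seen. The precision at stake matters most where groups are smallest, which is the race/ethnicity comparison that section 1.5 sizes the study for.

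**Working it through.** **The plan's own figure.** The 300 reproduces as three groups of 100. For a 1-df chi-square at w = 0.30 (the usual convention for medium, assumed here) and two-sided 0.05, the noncentrality at n = 100 is 100 × 0.30² = 9. Power is Φ(√9 − 1.96) = Φ(1.04) = 85.1%. With 400/3 ≈ 133 per group it is 93.3%. This is an unadjusted comparison of conditions within each group; baseline information plays no part in it.

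**Inputs from the documents.** N = 400, alpha 0.05, two conditions, three main race/ethnicity groups.

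**Assumed inputs.** 1:1 allocation, a two-sided test, r = 0.3 / 0.5 / 0.7, equal pre and post variances, equal groups of 133, an even or 30/70 split of white students and students of color, and effects in SD units. A medium effect is taken as 0.5 SD. As an alternative, w = 0.30 around a 50% base rate is a difference of 0.30 over an SD of 0.5, or 0.6 SD.

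**Variance relative to post-only.**
- ANCOVA: 1 − r² = 0.91 / 0.75 / 0.51
- Change score: 2(1 − r) = 1.40 / 1.00 / 0.60
- ANCOVA relative to change score: (1 + r)/2 = 0.65 / 0.75 / 0.85

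For any r strictly between 0 and 1, ANCOVA is below both.

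**Power** = Φ(effect/SE − 1.96). SE = √(4/n × factor) for a condition effect among n students. SE = √((4/n₁ + 4/n₂) × factor) for a difference in condition effect between two groups.

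| Comparison | Post-only | Change, r = 0.3 / 0.5 / 0.7 | ANCOVA, r = 0.3 / 0.5 / 0.7 |
|---|---|---|---|
| Overall, n = 400, 0.5 SD | 99.9% | 98.8 / 99.9 / >99.9% | 99.9% or more |
| Within group, n = 133, 0.5 SD | 82.2% | 68.3 / 82.2 / 96.1% | 85.6 / 91.5 / 98.1% |
| Within group, n = 133, 0.6 SD | 93.3% | 83.3 / 93.3 / 99.4% | 95.2 / 97.9 / 99.8% |
| Difference in effect, 200 v 200, 0.5 SD | 70.5% | 56.1 / 70.5 / 89.8% | 74.6 / 82.3 / 93.8% |
| Difference in effect, 120 v 280, 0.5 SD | 63.0% | 49.1 / 63.0 / 84.1% | 67.1 / 75.4 / 89.4% |

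At a fixed r, the best-to-worst gap among the three models in the 0.5 SD race/ethnicity rows is about 17 / 9 / 16 points (within group), 18.5 / 12 / 23 (even split) and 18 / 12 / 26 (30/70 split).

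A separate simulation of the difference in effect (133 v 267, 0.6 SD) gave post-only / change / ANCOVA power of 80 / 81 / 90% at r = 0.5 and 80 / 96 / 97% at r = 0.7. Type I error stayed near 5%.

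**The other item.** If it is yes/no (its response format is not in the text), the gain is smaller. In 3,000 simulated trials with N = 400, 50% yes and a difference of about 12 points, power was 67% unadjusted and 69 / 72 / 78% adjusted, with r on the underlying scale. The odds ratio moved from 1.63 to 1.67 / 1.73 / 1.89, because the adjusted one is conditional.

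**Why hypotheses 1 and 2 need separate models.** Hypothesis 1 says "students who report high levels of altruism will be more likely to report an intention to enroll". If altruism correlates 0.3 with intention at both times (assumed), its standardised coefficient falls from 0.30 to 0.3(1 − r)/(1 − 0.09) = 0.23 / 0.16 / 0.10 once pre-appeal intention is in the model.

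**The case against.** Section 6.1 does not exclude ANCOVA: linear regression can hold the pre-appeal answer, and asking the items twice suggests that it will be used. That stands. The gap is an unstated choice, not a wrong one.

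A reader might infer that an unadjusted analysis misses the 85% target within a race/ethnicity group. The documents do not support this. The 82.2% above arises only if medium is taken as 0.5 SD. On the w = 0.30 reading that reproduces the 300, unadjusted power is 85.1% at n = 100 and 93.3% at n = 133.

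A reader might also compare, say, 49% (change score, r = 0.3) with 84% (change score, r = 0.7) and conclude that model choice moves power by about 35 points. That is the effect of r. At a fixed r the gap is 9 to 26 points.

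Hypothesis 5 can be read literally as students of color against white students within the rational arm. Those groups are not randomised, so the precision argument does not cover that reading, and adjusting for pre-appeal intention would change the question. This stands and belongs in the fix.

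Finally, the gain depends on r, which the documents do not give. The background text shown between the two measurements could lower it. A lower r shrinks the gain over post-only but makes a change score worse, so the ranking that favours ANCOVA does not depend on r.

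**Conclusion.** This is a free improvement. It is not an error in the sample size and not a source of bias in the randomised contrast. For the likelihood rating, ANCOVA is more precise than post-only or change-score analysis at any r strictly between 0 and 1.

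- The overall comparison at the planned effect has about 99% power or more under all three models, so there is no practical difference there.
- Within a group of 133, ANCOVA adds about 3 / 9 / 16 points over post-only at 0.5 SD and about 2 / 5 / 6.5 points at 0.6 SD.
- For a 0.5 SD difference in condition effect between white students and students of color at N = 400, it adds about 4 / 12 / 23 points with an even split and 4 / 12 / 26 with a 30/70 split.

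The triples are for r = 0.3 / 0.5 / 0.7. The correlation, group sizes and SD effects are assumptions. The omission itself is plain from sections 1.3, 1.6 and 6.1.

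**What to change.** In section 6.1:

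1. Name the primary intention item and the post-appeal time point. The likelihood rating fits the linear models already named.
2. Compare it between conditions in a model with condition, the pre-appeal answer and sex (the randomisation factor). Use linear regression for the rating. If the other item is yes/no, use logistic regression and note that the odds ratio is conditional on the covariates.
3. Use the same covariates for the condition-by-race/ethnicity, condition-by-altruism and condition-by-knowledge terms. Report both the interaction and the condition effect within each race/ethnicity group. Do not read the adjusted main effects of altruism or knowledge as tests of hypotheses 1 or 2.
4. State that hypothesis 5 is tested as the difference in condition effect between students of color and white students. Report any comparison within the rational arm alone separately, as non-randomised.
5. Test hypotheses 1, 2 and 6 in separate models without the pre-appeal answer, and state which time point is their outcome.
6. Keep students who skipped only the pre-appeal item, by missing indicator or imputation, since section 4.7 E lets participants skip questions.

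The cost is a few sentences and about two model degrees of freedom out of about 400, with no new data and no added burden on participants.

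### H1, H2 and H6 do not say whether they use the pre-appeal or post-appeal intention score, and section 6.1 does not adjust the post-appeal outcome for the pre-appeal score

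*Combined protocol and SAP*

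**What the plan says.** Section 1.3 A gives the order of events. Demographics, personality measures, knowledge and a first intention measure come first. Then "All participants will then be given background information on bone marrow transplants", students are randomized to one of two appeals, and intention is asked again.

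Section 1.6 B states: "The primary dependent variable is intentions to register in the bone marrow transplant registry". It describes two intention questions and adds: "They will be asked these questions before and after the experimental manipulation". No time point or change score is named.

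Three hypotheses in section 1.1 B link a trait to intention without mentioning an appeal:
- H1: "students who report high levels of altruism will be more likely to report an intention to enroll in the stem cell transplant registry"
- H2: "students who report high levels of knowledge about stem cell transplants will be more likely to report an intention to enroll"
- H6: "self-esteem will differ between individuals who do and do not indicate an intention to enroll in the registry"

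Two others are worded as following an appeal:
- H3: "high altruistic students will be more likely to enroll when presented with an emotional appeal"
- H4: "high knowledge students will be more likely to enroll when presented with a factual appeal"

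Section 6.1 is one sentence. It names ANOVA and multivariate linear regression, and assigns no score, model or covariate to any hypothesis.

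**The concern.** Objective 1 in section 1.1 A is descriptive: which demographic, personality and psychosocial factors go with attitudes to the registry. Only the pre-appeal score is untouched by the study's own text and appeals. The post-appeal score answers a different question, namely which students intend to enrol after reading that material. Either score fits the wording of H1, H2 and H6, so three of the six hypotheses lack a defined outcome.

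The second gap concerns the randomized comparison. The pre-appeal score is likely to be a strong predictor of the post-appeal score and is already collected, but 6.1 does not say it will be used as a covariate. Leaving it out gives away precision in the arm comparison and in H3 to H5.

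**Working it through.** **The plan's own figure.** Section 1.5 gives 300 participants for 85% power at 0.05 with a medium effect. It does not state the method. One calculation reproduces it: a 1-df chi-square test with w = 0.30 within each of three race/ethnicity groups of 100. The noncentrality is 100 × 0.30² = 9 and the power is Φ(3 − 1.96) = 85.1%. (The cited w = 0.38 would give 63 per group, 189 in total.) In this reconstruction N rests on the condition comparison and takes no credit for a baseline covariate. Nothing below changes 300 or the target of 400.

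**What the post-appeal slope estimates (H1, H2).** Let s be the slope of pre-appeal intention on a standardized trait. Let the emotional and rational arms change that slope by bE and bR. With 1:1 allocation (assumed), the pooled post-appeal slope is s + (bE + bR)/2. H3 says only that bE exceeds bR for altruism, and H4 the reverse for knowledge. That fixes the sign of the difference but not of the average. For bE − bR = 0.2:
- bE = 0.2, bR = 0: pooled slope s + 0.10
- bE = 0.1, bR = −0.1: pooled slope s
- bE = 0, bR = −0.2: pooled slope s − 0.10

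**Size at N = 400, two-sided 0.05.** All effects here are assumed. Pre-appeal intention has variance 1 and prior correlation r0 with the trait (so s = r0), and the appeals differ by 0.3 SD on average. The post-appeal variance is V = 1 + 0.3²/4 + (bE² + bR²)/2 + r0(bE + bR) + noise variance. The post-appeal correlation is [r0 + (bE + bR)/2]/√V. Power is Φ(atanh(r)·√397 − 1.96).

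| r0 | bE | bR | noise SD | post r | rejects, pre score | rejects, post score |
|---|---|---|---|---|---|---|
| 0 | 0.1 | 0 | 0 | 0.05/√1.0275 = 0.049 | 5% | 16% |
| 0 | 0.2 | 0 | 0 | 0.10/√1.0425 = 0.098 | 5% | 50% |
| 0 | 0.3 | 0 | 0 | 0.15/√1.0675 = 0.145 | 5% | 83% |
| 0.20 | 0 | −0.2 | 0 | 0.10/√1.0025 = 0.100 | 98% | 51% |
| 0.10 | 0 | 0 | 0.5 | 0.10/√1.2725 = 0.089 | 52% | 43% |

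The first three rows show an association created by one appeal. The fourth shows one eroded by the other appeal. The fifth shows loss from noise alone.

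**H2 and the background text.** The knowledge score is taken before the text. If the text flattened the knowledge slope so that r fell from 0.20 to 0.15 or 0.10, power would go from 98% to 85% or 52%. The text is in Appendix A, which is not reproduced in the documents reviewed, so this is a scenario only.

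**H6.** Its groups are defined by the intention answer. Assume a standardized self-esteem difference d = 0.30 and 40% intending beforehand. Then z = 0.30 × √(160 × 240/400) = 2.94 and power is 84%. Suppose 10 points of students then move to yes regardless of self-esteem: d = 0.30 × 40/50 = 0.24, z = 0.24 × √(200 × 200/400) = 2.40, power 67%. For 20 points: d = 0.30 × 40/60 = 0.20, z = 0.20 × 9.80 = 1.96, power 50%. If movement depended on self-esteem, the contrast could grow instead.

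**Covariate gain.** With pre/post correlation ρ, adjusting for the pre-appeal score multiplies the residual variance of the arm comparison by about 1 − ρ². That is 0.75 at ρ = 0.5, 0.51 at 0.7 and 0.19 at 0.9. These values of ρ are assumed. For H3 and H4 the relevant ρ is the correlation remaining after the trait is in the model.

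**The case against.** The wording already leans towards the pre-appeal score. H3 and H4 condition on an appeal, whereas H1, H2 and H6 do not mention one, and the traits are collected alongside the first intention measure. Predicting intention after everyone has read the same text is also a legitimate question, since section 1.2 names lack of information as a main barrier. With randomized arms, a slope averaged over conditions is an ordinary main effect, and a main effect of the appeal does not by itself bias it. The traits are secondary independent variables, and the primary randomized contrast does not depend on which score H1, H2 and H6 use.

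All of this stands, and it limits the point. The lean in the wording supports the proposed default, but nothing in 1.6 or 6.1 makes it the rule.

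A reader might infer several stronger claims that the documents do not support:
- That the post-appeal score will be used for H1, H2 and H6. The plan does not say so.
- That it systematically weakens H2 or misclassifies the H6 groups. Both depend on assumed shifts, and the calculation shows rejection rates can rise as well as fall.
- That type I error is inflated by choosing the better of two scores. Reporting whichever of two scores correlated 0.7 is significant would give about 8.4% instead of 5%, but no such choice is planned.

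**Conclusion.** The point holds as a gap in specification with a clear preferred answer. The outcome time point is undefined for H1, H2 and H6, and baseline adjustment is unspecified for the arm comparison and H3 to H5. Using the post-appeal score for the three trait hypotheses would change the question and could move the association either way. In the scenarios shown, rejection ranges from 16% to 83% where there is no prior association, and power falls from 98% to about 51% where there is one. The interactions, noise, shifts and correlations are all assumptions, so these figures show what is possible and do not estimate what will happen. The pre-appeal score is the better choice because it is the only one untouched by the study materials and so fits Objective 1. The covariate adjustment is a gain in precision at no cost in data.

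**What to change.** Add to section 6.1:
- H1, H2 and H6 are tested on the pre-appeal intention score, with the H6 groups formed from the pre-appeal answer. Any post-appeal version is labelled a sensitivity analysis.
- The emotional-versus-rational comparison and H3 to H5 are analysed on the post-appeal intention score with the pre-appeal score as a covariate.

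The cost is two sentences of text, ideally fixed before the data are analysed. Both scores are already collected, so no items, participants or procedures are added, and the 300 and 400 in section 1.5 stay as they are.
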